9.2 Primary Efficacy Objective: Successful Percutaneous Localization of PPN

This is defined as the percentage of subjects in whom the nodule is successfully localized and removed in the first resected specimen. A pathological specimen with clear margins will count as a successful localization.

To evaluate the accuracy of percutaneous nodule localization using the SPiN Thoracic Navigation System™ and its accessories, by recording the percentage of successful nodule resections that result in the complete removal of the patient's nodule, with at least a one cell perimeter and negative margins. The diagnostic yield is calculated as the percentage of patients who have intra-operative localizations resulting in complete removal of nodule, divided by the total number of evaluable subjects.

Confirmation of Diagnosis

Surgical pathology results will determine the outcome of the primary endpoint. If the patient has follow-up imaging that shows a decrease in size or resolution of the nodule, the nodule will be determined to be of benign etiology if the study pathology yields a benign diagnosis (granuloma, inflammation, fibrosis, infection). To verify final diagnosis, a copy of the final pathology report will be de-identified and provided by the site. The pathology findings will then identify the case as either benign or malignant. Whether a benign or malignant diagnosis is made, the primary endpoint is met.

If Margins are Intact

If the nodule has intact margins as described by the pathology report. Explicitly, a perimeter of at least one cell around the nodule contain cells that are all non-malignant. This plus the nodule sample verifies that the entire nodule was removed. The pathology findings will then identify the case as either benign or malignant.

Crossover Cases

It is anticipated that there will be cases where the wedge is positive for malignancy and the deep margin also will be positive. In these cases, the surgical plan may change from a planned wedgeectomy into a completion lobectomy or segmentectomy. If the nodule is fully removed

(having at least a cell's margin of non-malignant cells in these cases, then the primary endpoint is met. The pathology findings will then identify the entire case as either benign or malignant, and the primary endpoint is met.

Margins for Crossover Cases

If the nodule is fully removed in crossover cases, then the primary endpoint is met. The nodule may be removed per the surgeon's judgement. The pathology findings will then identify the entire case as either benign or malignant, and the primary endpoint is met.

If Diagnosis is Non-malignant

If the nodule is deemed non-malignant, cells are identifiable, then the positive box for diagnosis is checked, and:

- The nodule must have an intact margin of a cell as a perimeter to be diagnostic.
- The type of nodule (ground glass opacity, etc.) is collected from the pathology report.

The pathology findings will then identify the case as either benign or malignant.

9.3 Safety Objective:

Record Safety Events During Intraoperative Percutaneous Localization Only

To collect and evaluate the safety of nodule localization, including incidence and severity of localization-procedure related adverse events (AEs) and serious adverse events (SAEs) that occur during the localization procedure.

Baseline/Enrollment

All patients will be provided with information about the registry and will sign the informed consent form before any registry-related assessments are made. The following data will be collected at baseline for all enrolled patients:

- To be collected at baseline visit: Review of inclusion/exclusion criteria.

Localization Period

- The localization period begins when the needle touches the subject's skin.
- Localization ends when the localization needle is withdrawn from the subject for the final time.
- Any adverse events that develop during the localization procedure will be reported.
- Bronchoscopy-related events that occur during the alignment of the CT with the patient ("registration") will be recorded.
- Percutaneous localization step, injection of dye, injection of any microcoils, etc.

The process used for AE reporting conforms to Veran Medical Technologies, Inc., standard operating procedures (SOPs) for Medical Device Reporting (MDR)(Appendix C). Training on AE/SAE/MDR reporting practices will be provided to each participating site.

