--	---

	PHI and privacy. All data collected into the study database will be de-identified at the site level.
STUDY PROCEDURES	
Subjects are treated for lung resection according to the treatment devised by their clinician.
 
Part of the technical procedure registry trains thoracic surgeons on the various available tools and techniques in intraoperative localization, using both didactic review, best practices, case review, and a cadaver lab.
 
The following represents the typical standard of care for this procedure. The registry study is nested within the standard lung resection operation, and study procedures on data collection are described within the context of these procedures for clarity of identification:
 
Following nodule identification and referral, subjects are typically evaluated per the subject inclusion/exclusion criteria. Review of the subject's CT/PET scan demonstrate a PPN that is between 0.4 cm and 3.2 cm in its longest dimension. All subjects will sign and date an Informed Consent Form (ICF) before enrollment (Baseline Visit).
 
Subjects will undergo a chest CT scan on the day of surgery, verifying the longest dimension of the nodule (data collected). The subject is put under general anesthesia. The SPiN Percutaneous nodule localization procedure is performed intraoperatively, using dye and/or other localization techniques. A surgical resection (wedge, segmentectomy etc.) will follow, according to PI's judgment. Subjects are generally hospitalized between 2-5 days following this procedure and discharged. Following discharge, subjects typically follow a schedule of multiple clinic visits, as determined by their healthcare team. Subject participation in the localization registry will end following hospital discharge.

ESTIMATED DURATION OF STUDY	The Registry is anticipated to take 24 months to complete.

STUDY POPULATION	
The target subject population includes adult subjects (18 years-85 years), with PPNs. In the judgment of the thoracic surgeon, localization for resection is warranted via a percutaneous localization approach. The establishment of malignancy is not necessary for PPN removal.
 
Data will be collected from study subjects having a PPN between 0.4 cm and 3.2 cm in greatest dimension, that are accessible to percutaneous localization, who consent to and undergo intraoperative dye/wire localization procedure followed by surgical lung resection.

-------------------------	--

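### Section 9.2 declares the primary endpoint met on any benign or malignant diagnosis, which contradicts the removal-and-margin definition and leaves a benign wedge that missed the target open to opposite scoring

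*Combined protocol and SAP*

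**What the plan says.** The primary endpoint is defined in the Synopsis (Primary Objective), Section 4.1 and Section 9.2 as "the percentage of subjects in whom the nodule is successfully localized and removed in the first resected specimen". Each place adds: "A pathological specimen with clear margins will count as a successful localization". Sections 4.1 and 9.2 also speak of complete removal with negative margins, and Section 9.2 adds a perimeter of at least one cell.

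Under Confirmation of Diagnosis, Section 9.2 begins with "Surgical pathology results will determine the outcome of the primary endpoint". It then gives an imaging rule, "follow-up imaging that shows a decrease in size or resolution of the nodule, the nodule will be determined to be of benign etiology", subject to a condition: "if the study pathology yields a benign diagnosis (granuloma, inflammation, fibrosis, infection". After asking for the de-identified pathology report, the paragraph closes: "Whether a benign or malignant diagnosis is made, the primary endpoint is met".

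For benign cases, the later paragraph If Diagnosis is Non-malignant says: "The nodule must have an intact margin of a cell as a perimeter to be diagnostic".

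On follow-up, the Synopsis (Study Procedures) says: "Subject participation in the localization registry will end following hospital discharge". Table 1 has columns for the baseline visit and Day 0 only.

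**The concern.** The endpoint is about getting the target out in the first piece of tissue. The closing sentence of Confirmation of Diagnosis replaces this with a different criterion, namely that pathology returned a diagnosis. The two come apart where the doubt is greatest: a benign specimen that may not contain the target. Inflammation and fibrosis are on the protocol's own list of acceptable benign results, and a wedge taken beside the nodule could show either.

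The imaging clause might look like a safeguard for such cases, but it carries no information about removal. It resembles a rule for a biopsy study, where the nodule stays in the lung and its later course supports a benign sample. That origin is an inference; the section does call its endpoint a diagnostic yield, the term that Sections 2 and 7 use for biopsy studies.

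At stake is whether the primary proportion has one meaning. Two people scoring the same chart from Section 9.2 could reach opposite answers, and the permissive reading can only push the rate up.

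**Working it through.** The plan gives no figure to reproduce: there is no target success rate, and Section 11.1 states that the sample size was not formally estimated. The check is therefore a comparison of the rules, followed by the arithmetic of one mis-scored case.

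**Step 1. One case under each rule.** Take a subject whose wedge missed the target. Pathology reports inflammation only, and the nodule is still in the lung.

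| Rule | Place | Score |
|---|---|---|
| Nodule removed in the first specimen | Synopsis; 4.1; 9.2 | Failure |
| Complete removal, one-cell perimeter, negative margins | 9.2 | Failure |
| One-cell margin for a non-malignant nodule | 9.2, If Diagnosis is Non-malignant | Failure: no nodule to have a margin |
| Specimen with clear margins | Synopsis; 4.1; 9.2 | Unclear: taken alone, could be read to pass a benign wedge |
| Any benign or malignant diagnosis | 9.2, Confirmation of Diagnosis | Success |

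The success in the last row needs no imaging. No rule says which row governs, and none requires the lesion in the specimen to be matched to the target on CT.

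**Step 2. What the imaging clause can add.** The timing of the imaging is not defined. If it is post-operative:

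- Resolution is expected after any complete removal, benign or malignant, so it does not bear on etiology.
- A decrease in size suggests that nodule remains, which is evidence against the endpoint.
- No such scan is scheduled. The Synopsis gives a usual stay of 2-5 days, and participation ends at discharge, so the clause could be applied only to subjects who happen to have a later scan on file.

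**Step 3. Size per case.** The inputs are n = 70 to 100 evaluable subjects (Section 11.1) and a denominator of evaluable subjects (Section 4.1). The change in the rate per mis-scored case is 100/n percentage points:

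- n = 70: 100/70 = 1.43
- n = 100: 100/100 = 1.00

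**Step 4. Illustration with exact (Clopper-Pearson) 95% intervals.** The true success rates and the numbers of mis-scored cases are assumptions; the documents give neither.

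| Assumed true rate | n | Mis-scored | Reported | 95% interval |
|---|---|---|---|---|
| 90% | 70 | 0 | 63/70 = 90.0% | 80.5-95.9 |
| 90% | 70 | 2 | 65/70 = 92.9% | 84.1-97.6 |
| 90% | 70 | 5 | 68/70 = 97.1% | 90.1-99.7 |
| 90% | 100 | 0 | 90/100 = 90.0% | 82.4-95.1 |
| 90% | 100 | 2 | 92/100 = 92.0% | 84.8-96.5 |
| 90% | 100 | 5 | 95/100 = 95.0% | 88.7-98.4 |
| 80% | 70 | 2 | 58/70 = 82.9% | 72.0-90.8 |
| 80% | 100 | 2 | 82/100 = 82.0% | 73.1-89.0 |

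One or two such cases move the estimate by much less than its interval is wide.

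**The case against.** The best defence is that Section 9.2 should be read as a whole. The definition comes first, and the benign rule makes an intact margin a condition of being diagnostic. On that reading a wedge without the nodule yields no qualifying diagnosis, and the case fails. This has force: the documents do not plainly score misses as successes. It does not remove the conflict. The closing sentence is unconditional, nothing gives the margin rules precedence, and the one-cell rule presupposes that the pathologist has the target in hand.

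It can also be said that this is a descriptive registry with no hypothesis test, so no decision turns on a point or two. That is true and limits the consequence. The primary proportion is still the main result, and it needs a single definition.

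A reader might go further in three ways that the documents do not support.

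- **That the imaging clause itself turns a missed, self-resolving nodule into a success.** The clause assigns etiology, only when pathology is already benign, and the paragraph makes pathology decisive. The route to success is the closing sentence, with or without a scan. Because the timing is undefined, the imaging could even be pre-operative.
- **That the primary rate is biased upward.** Only the possibility is shown. Scorers who follow the definition would count these cases as failures.
- **That some 13 to 98 subjects are affected.** Section 2 cites 2-82% malignancy, so 18-98% benign gives 0.18 × 70 = 12.6 to 0.98 × 100 = 98. That counts every benign subject, and the cited range is for incidentally detected nodules, not for patients selected for resection. A case is mis-scored only if the wedge missed the target and the permissive sentence was applied.

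**Conclusion.** The point holds as a contradiction between scoring rules in the primary endpoint. Confirmation of Diagnosis grants success on a diagnosis alone; the definition and the benign margin rule require removal. A benign wedge that missed the target can be scored either way, and the imaging clause cannot settle it.

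The size is 1.0 to 1.4 percentage points per mis-scored case, always upward. The total effect cannot be stated, because the documents give no expected number of misses or of benign results without an identified target. Confidence is high that the rules conflict and low on how much the reported rate would change. The remark that shrinkage suggests residual nodule assumes post-operative imaging. The correction should be made, since it is cheap and it fixes what the primary rate means.

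**What to change.** In Section 9.2, Confirmation of Diagnosis, replace the closing sentence ("Whether a benign or malignant diagnosis is made, the primary endpoint is met") with:

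> *The primary endpoint is met, for a benign or malignant diagnosis, only if the pathology report confirms a lesion consistent with the target nodule on the planning CT in the first resected specimen, with clear margins.*

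Delete the imaging sentence, or limit it to describing etiology. Report any later imaging that shows a residual target descriptively. It should not define failure, because only some subjects will have it. Nor should inflammation or fibrosis count as an automatic failure, since a correctly resected inflammatory target may show just that.

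The two crossover paragraphs of Section 9.2 should be reconciled in the same edit. They grant success on full removal after the surgical plan changes, which does not sit with a first-specimen criterion.

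The cost is protocol wording and one eCRF item (specimen lesion matches target: yes/no). Nodule size and location on CT (Section 9) and the final pathology report (Section 9.2) are already collected. The reported success rate may be slightly lower.

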Localization of the peripheral nodules in the outer lung regions can be accomplished intraoperatively, just prior to surgical resection, with the same surgical staff who are performing the operation. This eliminates an additional step for the thoracic surgeon (or other oncology team member) and also for the subject, namely identifying and coordinating with persons from other departments who may typically place fiducial, hookwire, and microcoils as separate procedures, involving additional resources. In addition, the migration of these markers, and the need to verify their placement with an additional CT or other scan prior to surgery, are potentially steps that may be able to be streamlined. The overarching objective is to keep this localization and resection procedure within the hands of the principal investigator, and to quantify the percentage of subjects in whom the nodule is removed in the first resected specimen, procedure time, and nodule characteristics and procedure details and techniques.

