4. OBJECTIVES

The registry is aimed at developing a high-quality set of data regarding the percutaneous localization of PPNs. The localization registry itself is nested within the subjects' lung resection operation. Analyzing and promulgating evidence-based best practices for lung nodule localization will allow surgeons to identify technical solutions and reproducible methods.

This registry will record procedural data for trained thoracic surgeons using the SPiN Thoracic Navigation System™ and tools. Diagnostic yield will measure successful localization of the lesion in the resected specimen. Localization-related safety events will be collected.

4.1 Primary Objective:

Successful percutaneous localization of PPN.

To evaluate the accuracy of percutaneous nodule localization using the SPiN Thoracic Navigation System™ and its accessories, Veran will record the percentage of successful resections that result in the complete removal of the patient's nodule, with a negative margin. The diagnostic yield is calculated as the percentage of patients who have intra-operative localizations resulting in complete removal of nodule, divided by the total number of evaluable subjects. Evaluable subjects are those who complete the localization procedure.

Primary Objective: Successful percutaneous localization of PPN.

This is defined as the percentage of subjects in whom the nodule is successfully localized and removed in the first resected specimen. A pathological specimen with clear margins will count as a successful localization.

4.2 Safety Objective:

Collect safety data for localization procedure.

4.3 Secondary Objectives:

Secondary Objectives: Use as per synopsis – including margin.

- 4.3.1 Report localization methods and techniques – dye and materials used, volume of dye (methylene blue, ICG etc.), other materials such as microcoils, hook wires etc. Details regarding these techniques will be collected.
- 4.3.2 Collect data on intraoperative percutaneous localization time and duration of total surgical procedure.
- 4.3.3 Record nodule characteristics, including location in the lobe, distance from pleura, distance from surface of skin to target, morphological appearance, solid vs. ground glass etc.
- 4.3.4 Record weight of excised tissue and margin.
- 4.3.5 Report type of surgical resection performed (segmentectomy or wedge) and resection technique (VATS, RATS, thoracotomy).

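### The primary endpoint requires removal in the first specimen, but the crossover rule counts a positive-margin first wedge as a success once later surgery removes the nodule

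*Combined protocol and SAP*

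**What the plan says.** The primary objective is worded the same way in the Synopsis, Section 4.1 and Section 9.2: "This is defined as the percentage of subjects in whom the nodule is successfully localized and removed in the first resected specimen". In each place the next sentence adds that a pathology specimen with clear margins counts as a success. Section 2 gives the same aim: "to quantify the percentage of subjects in whom the nodule is removed in the first resected specimen". Sections 4.1 and 9.2 also speak of complete removal with negative margins, and Section 9.2 asks for a perimeter of at least one cell.

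Section 9.2 then turns to crossover cases: "It is anticipated that there will be cases where the wedge is positive for malignancy and the deep margin also will be positive". The operation may be extended to a completion lobectomy or segmentectomy, and the endpoint counts as met if the nodule is then out with at least a one-cell non-malignant margin. The next paragraph, on margins in crossover cases, restates the rule without the margin condition: "If the nodule is fully removed in crossover cases, then the primary endpoint is met".

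Two other sentences bear on scoring. The calculation sentence in Section 4.1, repeated in Section 9.2, names no specimen: "The diagnostic yield is calculated as the percentage of patients who have intra-operative localizations resulting in complete removal of nodule", over evaluable subjects. Under the confirmation of diagnosis, Section 9.2 says: "Whether a benign or malignant diagnosis is made, the primary endpoint is met".

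On data, Section 9.2 says "To verify final diagnosis, a copy of the final pathology report will be de-identified and provided by the site". Section 4.3.4 says "Record weight of excised tissue and margin", without naming the specimen. Section 9 collects the planned and the eventual surgery.

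**The concern.** The crossover case that the protocol describes is one where the first specimen did not take the nodule out with clear margins. Under the definition it is a failure; under the crossover rule it is a success. The two rules also measure different things. The first asks whether localization led the surgeon to remove the nodule at the first attempt. The second asks whether the nodule was eventually cleared by whatever surgery was needed.

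This rate is the registry's main efficacy result. Two analysts, or two sites, applying different paragraphs of Section 9.2 would report different rates and different 95% confidence intervals from the same patients. The protocol expects such cases, so this is not a remote possibility. Section 11.1 states that no formal hypothesis is tested, so no error rate or success threshold is involved.

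**Working it through.** The plan gives no expected success rate, crossover rate or sample-size calculation (Section 11.1), so there is no figure to reproduce. The check is to apply each rule to each type of subject and then see what the difference does to the rate.

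**Scoring by type of subject**

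| Subject | First-specimen definition | Crossover rule |
|---|---|---|
| Whole nodule in first specimen, margins negative | success | success |
| As above, then operation changed for another reason | success | success |
| First wedge malignant, deep margin positive, nodule cleared by completion surgery | **failure** | **success** |
| Nodule never fully removed | failure | failure |

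Only the third row differs. Section 9 uses the term crossover for any change from planned to eventual surgery, so most kinds of crossover need not contribute to the discrepancy.

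**Size of the difference**

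Let N be the number of evaluable subjects, *a* the first-specimen successes and *b* the subjects in the third row.

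- Rate under the definition: *a*/N
- Rate under the crossover rule: (*a* + *b*)/N
- Difference: *b*/N, which is never negative and does not depend on *a*

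Section 11.1 gives N as 70 to 100. Each such case therefore moves the rate by 100/100 = 1.00 percentage point at N = 100, or 100/70 = 1.43 points at N = 70.

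**Illustration**

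The values of *a* and *b* below are assumptions. Intervals are exact (Clopper-Pearson) for x successes in N: the lower limit is the 0.025 quantile of Beta(x, N − x + 1) and the upper limit is the 0.975 quantile of Beta(x + 1, N − x). The plan does not name an interval method.

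| N | *a* | *b* | (*a* + *b*)/N | Rate | Exact 95% CI |
|---|---|---|---|---|---|
| 100 | 85 | 0 | 85/100 | 85.0% | 76.5 to 91.4 |
| 100 | 85 | 2 | 87/100 | 87.0% | 78.8 to 92.9 |
| 100 | 85 | 5 | 90/100 | 90.0% | 82.4 to 95.1 |
| 100 | 85 | 10 | 95/100 | 95.0% | 88.7 to 98.4 |
| 70 | 60 | 0 | 60/70 | 85.7% | 75.3 to 92.9 |
| 70 | 60 | 2 | 62/70 | 88.6% | 78.7 to 94.9 |
| 70 | 60 | 4 | 64/70 | 91.4% | 82.3 to 96.8 |
| 70 | 60 | 7 | 67/70 | 95.7% | 88.0 to 99.1 |

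The *b* = 0 rows are the rate under the definition; the others are what the crossover rule would report from the same patients. Because the two rates are nested in one set of subjects, the difference in points is the right measure, and overlap of the intervals says nothing useful.

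**The case against.** The strongest reply is that Section 9.2 does not leave crossovers open. It gives an explicit rule for exactly this case, twice, and a specific rule is ordinarily read as overriding a general definition. On that reading the rate can be computed, and the fault is only a definition that fails to mention its exception. But the document states no such order of precedence, and this reading would strip the first-specimen condition of effect in the very cases where it matters.

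A second reply is that the sentence on clear margins could refer to any specimen, and that a malignant wedge shows the nodule was at least partly reached. It is true that first specimen and clear margins are joined by reading adjacent sentences together. However, the definition requires removal as well as localization, Sections 4.1 and 9.2 ask for complete removal with a negative margin, and the crossover text itself makes success depend on later surgery getting the nodule out.

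Third, Section 11.2.1 defers the analysis to a written SAP, and under Section 12.5 only the sponsor or its designee holds the pooled data. Central scoring would limit inconsistency between sites, but no SAP text in the combined document chooses between the rules.

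Several points do stand. The true size of the shift is unknown, and the larger shifts illustrated have no basis in the documents. The registry is descriptive. The data form is not in the supplied text, so whether it captures first-specimen margins cannot be judged. Rewriting the definition to admit the exception would also remove the contradiction, though the rate would then describe eventual surgical clearance rather than what the Synopsis and Sections 2, 4.1 and 9.2 say is to be measured.

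**Conclusion.** The concern holds. The primary endpoint has two numerators that disagree on a type of case the protocol expects, and nothing in the document settles which applies. Relative to the stated definition, the crossover rule can only raise the rate, by 1.00 point per affected subject at N = 100 and 1.43 at N = 70. Those per-case figures follow from the planned sample size alone. The total shift depends on how many positive-margin first wedges are later cleared, which the documents do not say; with none, the two rules agree. The consequence is for the interpretation and reproducibility of the primary rate and its confidence interval, not for any test. It must be fixed before the primary rate is reported.

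**What to change.** Use one first-specimen numerator throughout:

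1. In Section 9.2, score a subject whose first specimen does not contain the whole nodule with negative margins as not meeting the primary endpoint, even if a later resection completes the removal.
2. State that a change of operation after a margin-negative first specimen remains a success.
3. Add the first-specimen condition to the calculation sentence in Sections 4.1 and 9.2.
4. Report eventual complete removal, crossovers included, as a separate secondary rate, with the number of subjects on whom the two rates differ.
5. Keep the sentence that benign and malignant diagnoses both count, but make it conditional on the first-specimen and margin criteria.
6. Confirm that the data form records first-specimen margin status separately from the final pathology report, and add the field if it does not.

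The cost is protocol and SAP wording and possibly one data field. Pathology reports of subjects already treated may need to be re-read, and the headline rate may be somewhat lower than under the crossover rule. Eventual removal is still reported, so no information is lost. The change concerns endpoint scoring only and leaves surgical management alone.
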